## Why or why not?

## Appendix C. Nuclear medicine staff questionnaire for post-procedural pain

Patient Study ID \_\_\_\_\_

### Pain Control for Breast Cancer Patients Undergoing Sentinel Lymph Node Biopsy Research Study

#### Provider Survey for Post-Injection Patients

1) Did the patient arrive with a lidocaine patch on the breast?

[figure not shown]
- Yes
- No but patient in a lidocaine patch treatment arm
- Not applicable- patient NOT in lidocaine patch treatment arm

2) Did the patient require more than one radiocolloid injection?

- Yes
- No

3) Ease of administration:

[figure not shown]
Overall, how difficult or easy was it to administer the intervention? Circle a number on the 7-point rating scale below:

4) Pain score of patient:

This question is interested in your perspective of the patient's pain intensity during the injection. Please do not ask the patient for a numeric pain score for the purposes of answering this question.

Please indicate on the following scale with an X where you think the patient's pain intensity was related to the radiotracer injection.

## Appendix D. Nuclear medicine staff questionnaire upon study completion

Provider study ID \_\_\_\_\_

### Pain Control for Breast Cancer Patients Undergoing Sentinel Lymph Node Biopsy Research Study

#### Provider End-of-Study Survey

The following questions are regarding the randomized study of topical pain treatments for the radiotracer injections for sentinel lymph node mapping in breast cancer patients.

1) Rank the following pain treatments in order of easiest (1) to administer to hardest (4) to administer. Use each number 1-4 only once.

\_\_\_\_\_ Ice pack to the breast

\_\_\_\_\_ Lidocaine patch to the breast

\_\_\_\_\_ Ice pack to the breast with Buzzy

\_\_\_\_\_ Lidocaine patch to the breast followed by ice pack to the breast with Buzzy

2) Rank the following pain treatments in order of what you think provided the best pain control (1) to what you think provided the least pain control (4). Use each number 1-4 only once.

\_\_\_\_\_ Ice pack to the breast

\_\_\_\_\_ Lidocaine patch to the breast

\_\_\_\_\_ Ice pack to the breast with Buzzy

\_\_\_\_\_ Lidocaine patch to the breast followed by ice pack to the breast with Buzzy

3) Please describe any challenges, if applicable, to implementing any of the pain treatments (open response):

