Post-procedural survey: The first survey will be to assess the nuclear medicine technologists' immediate perception of the ease of administration of the intervention and the patient's post procedural pain (Appendix D). Each post-procedural survey will be linked to the patient study ID. This will be completed by the technologist assisting with each enrolled patient.

Nuclear Medicine Technologists will be providing ancillary and/or standard of care services that are within their normal scope of clinical practice. As part of their normal scope of practice and standard of care, technologists assist Nuclear Medicine MD, DOs with radiotracer injections and associated pain control/pain mitigation procedures. Technologists who assist with study participants will be included in the study team.

End-of-study survey: We will also administer a brief survey at the end of the trial to the nuclear medicine faculty and technologists involved in the radiotracer injection and associated pain control for patients on the trial. The nuclear medicine faculty and technologists will be the staff most consistently involved in the injections throughout the study time period and therefore would be most reliably able to reflect on implementation of the interventions. (Appendix E).

Nuclear Medicine faculty are ultimately responsible for and supervise each radiotracer injection and associated pain control. They serve an integral role in the conduct of research-specific study procedures and are included in the study team.

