## 7. MEASURES

*Primary patient outcome measure:* The Wong-Baker FACES pain rating scale is a standardized 10-point Likert scale that is validated and has utility for patients with lower health literacy (27,28). It has been used in prior studies assessing pain with radiotracer injection for SLN mapping (9–11) (Appendix A).

*Secondary patient survey outcome measures:*

- Short Form McGill questionnaire: This is a validated pain questionnaire taking an average of 2-5 minutes to complete that captures subjective experiences of pain in both sensory and affective categories on a 4-point Likert scale. A total score out of 45 is calculated with sensory and affective sub-scores (29) and has been used in prior studies assessing pain with radiotracer injection for SLN identification (9–11) (Appendix B).
- We will ask questions to determine whether the patient received their intervention as assigned (Appendix B).
- Questions to assess patient experience and satisfaction were drawn from the following:
  - Consumer Assessment of Healthcare Providers and Systems (CAHPS®) questions Surgical Care survey (30) (Appendix B).
  - The American Society of Anesthesiologists Satisfaction with Anesthesia Questions (31) (Appendix B).
  - Studies of patient experience/satisfaction with local analgesia using validated surveys (32–34)(Appendix B)
- Recommendation of topical anesthetic option: We will ask patients whether they would recommend the topical anesthetic option that they received to others (yes/no) and inquire why or why not (open ended)(Appendix B).

*Secondary staff outcome measures:*

- Intervention usability and perceived patient pain:
  - The question to assess intervention usability is adapted from the Single Ease Question developed for assessment of usability after the completion of a task (31). The question addressing perceived patient pain utilizes the Numeric Rating scale (NRS), a validated pain rating scale used previously in provider assessment of patient pain with radiotracer injection (2,32). (Appendix C)
- End of study assessment:
  - The goal of the survey will be to assess experiences with implementing each arm of the study and any identified barriers. Nuclear medicine providers will be asked to rank order the usability and perceived efficacy of the different interventions. Space will be provided for open ended comments on benefits or barriers related to the interventions. (Appendix D)

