## 8. Statistical Considerations

### 8.1 Analysis

Data will be analyzed with intervention arms masked. All scales will be constructed in a manner consistent with scale development, including item non-response. We will compare mean post-procedural pain scores (primary outcome) and other continuous secondary outcomes with ANOVA, testing the null hypothesis that mean post-procedural pain scores will not statistically differ between the control and intervention arms. Pairwise differences between each of the intervention arms and the control arm will be assessed with t-tests. Differences in potential control measures between patients randomized to the control and intervention arms that arise by chance will be examined using a chi-square test or Fisher's exact test for categorical variables and analysis of variance (ANOVA) or Kruskal-Wallis test for continuous variables (depending on distribution), respectively. Should there be significant differences in control measures between arms, an analysis of covariance (ANCOVA) will be used to assess the primary outcome, including significant covariates. Differences in the secondary dichotomous measures (sentinel lymph node mapping, patient recommendation) will be assessed with Chi-Square analysis. We will summarize responses to open ended questions in the patient survey and adherence to intervention. All analyses will follow an intention to treat approach. We will summarize the responses from the nuclear medicine providers/staff to determine what arm was perceived to be the most effective method for pain control and the easiest to administer.

Secondary analysis will be performed on the type of radiotracer received and pain scores.

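### The end-of-study provider survey forces a full ranking of the four arms without recording which arms the rater used, so some ranks may be for arms never seen

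*Combined protocol and SAP*

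**What the plan says.** Section 5.7.2 sends the end-of-study survey "to the nuclear medicine faculty and technologists involved in the radiotracer injection and associated pain control for patients on the trial". It justifies the choice of raters by calling them the "staff most consistently involved in the injections throughout the study time period". It sets no minimum number of patients or arms per rater.

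Section 7 states the task: "Nuclear medicine providers will be asked to rank order the usability and perceived efficacy of the different interventions". The form in Appendix D (cited as Appendix E in section 5.7.2) has two ranking items, one for ease of administration and one for pain control. Each carries the instruction "Use each number 1-4 only once". A third item invites free text on challenges.

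Section 8.1 summarises provider and staff responses "to determine what arm was perceived to be the most effective method for pain control and the easiest to administer". It does not restrict or weight them by the rater's experience.

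The technologist who assists with a patient also completes the Appendix C form, which covers ease of administration and perceived patient pain. "Each post-procedural survey will be linked to the patient study ID", and the printed form shows only a "Patient Study ID" field. Appendix D shows only a provider ID. Under section 5.7.2, faculty complete the end-of-study survey and nothing else.

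**The concern.** A complete 1-to-4 order with no opt-out obliges a rater to place an arm even without having worked with it. Such a rank can reflect only expectation, for instance that the combined arm must work best or be the most trouble, yet it counts the same as a rank based on experience. Because Appendix C carries no provider ID and Appendix D asks nothing about exposure, the analyst could not separate the two kinds of rank from these forms.

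What is at stake is the secondary objective on barriers to implementation, and the statement in section 8.1 about which arm staff found most effective and easiest. No hypothesis test depends on the ranking.

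**Working it through.** The plan gives no figure on rater exposure, so there is none to reproduce. The check asks how likely a rater is to miss an arm at a given caseload.

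**Inputs from the documents.** Four arms (section 5.5); 40 patients per arm, 160 in total (section 8.2).

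**Assumptions.** The documents state neither the number of raters nor their caseloads, so both are varied. Patients reach raters without regard to arm. Every patient receives the assigned arm. Each patient is attended by one rater of a given type (one technologist, one faculty member), so R is the number of raters of one type.

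**Formula.** For a rater who attends k of the 160 patients, inclusion-exclusion over the four arms gives

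P(k) = [4·C(120,k) − 6·C(80,k) + 4·C(40,k)] / C(160,k).

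**Example, k = 4.** (4 × 8,214,570 − 6 × 1,581,580 + 4 × 91,390) / 26,294,360 = 23,734,360 / 26,294,360 = 0.903. The direct route agrees: seeing all four arms in four patients has probability 40⁴ / 26,294,360 = 0.097, and 1 − 0.097 = 0.903.

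**Equal sharing of 160 patients among R raters** (k rounded down):

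| R | k | P(k) | Expected raters missing an arm, R × P(k) |
|---|---|---|---|
| 5 | 32 | 0.0001 | about 0 |
| 8 | 20 | 0.008 | 0.07 |
| 10 | 16 | 0.031 | 0.3 |
| 15 | 10 | 0.200 | 3.0 |
| 20 | 8 | 0.358 | 7.2 |
| 30 | 5 | 0.757 | 22.7 |

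P(k) falls below 5% at k = 15 and below 1% at k = 20. With ten raters, the chance that at least one misses an arm is about 1 − (1 − 0.0305)¹⁰ = 27%, treating raters as independent.

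**Sensitivity to the sampling model.** If each patient's arm is instead an independent draw with probability 1/4, P(k) = 4(0.75)^k − 6(0.5)^k + 4(0.25)^k. This gives 0.906, 0.377, 0.219 and 0.040 for k = 4, 8, 10 and 16, against 0.903, 0.358, 0.200 and 0.031 above. The conclusion does not change.

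**Unequal caseloads.** A rater with fewer than four patients has missed at least one arm with certainty, so a few occasional raters can add unseen-arm ranks even where the average caseload is high.

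**Delivery as assigned.** Under section 5.6, a patient in Group C or D who arrives without a patch is treated without it, and under section 5.6.1, patients in those arms who are moved to a day-before injection are withdrawn. True exposure to the patch arms is therefore somewhat lower than the table assumes. The patch is also applied in preoperative holding (section 5.6), so nuclear medicine staff may rank its ease of administration without having applied one.

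**The case against.** Four points can be made for the plan.

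First, the authors did consider experience: section 5.7.2 chooses these staff as the most consistently involved and says that faculty supervise every injection. This stands as a rationale, but it is an expectation and not an eligibility rule, and it does not imply that each individual will have met all four arms.

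Second, a reader might infer that the rankings do contain guesses. The documents do not support this. With a small, stable team nearly everyone would see every arm; with no rater numbers or caseloads stated, it is a possibility only.

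Third, a reader might take the ranking to be the only provider comparison of the arms. It is not. The technologists' ratings of ease and perceived pain are made case by case and tied to the patient ID, hence to the randomised arm, and the reference in section 8.1 to provider and staff responses is wide enough to include them. The ranking is the sole structured source for faculty only.

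Fourth, the missing provider ID on Appendix C shows that exposure cannot be rebuilt from the forms as printed. It does not show that no other record could supply it.

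It is also fair to say that the survey asks for perception by design and is purely descriptive. That limits the weight of the point. It does not give a reason to require a rank for an arm the rater did not use.

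**Conclusion.** The point holds as a gap in the instrument. The form requires complete rankings, provides no opt-out and keeps no record of exposure, so ranks for unseen arms may enter the summary and would not be identifiable from the forms as shown. On even sharing of 160 patients, the effect is negligible with about ten raters or fewer of one type (0.3 of 10 expected to miss an arm) and material with many raters (about 7 of 20) or occasional ones. These figures rest on assumed rater numbers and on patients being distributed without regard to arm.

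The practical weight falls mainly on faculty. For technologists, the per-patient ratings already give a comparison by arm that rests on direct experience. This is a cheap improvement to a descriptive secondary outcome; the primary analysis and the sample size are untouched.

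**What to change.** In Appendix D, ask for each arm how many study patients the rater attended (0 / 1–2 / 3 or more), and allow *did not use* in place of a rank in both ranking items.

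In section 8.1, state that the rankings will be shown for all responders and for those who attended at least one patient in every arm, with the number of raters behind each arm, set beside the per-patient technologist ratings by arm. Neither set need be declared the main one: the restricted set could be small, and one patient per arm is a low and somewhat arbitrary threshold.

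Adding a provider ID to Appendix C would not replace the exposure question, because faculty never complete that form.

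The cost is a small edit to one form, a sentence in section 8.1 and one extra descriptive table. Some rankings will be incomplete, and the exposure counts will rest on recall at the end of the trial. If every rater turns out to have seen every arm, the two sets coincide and the report can say so.
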